3. To assess the impact of co-administration of *Na*-GST-1 and *Na*-APR-1 (M74) on the functional capacity of vaccine-induced antibodies to neutralize the *in vitro* activity of the native enzymes (*Na*-GST-1 and wild type *Na*-APR-1).
4. To assess the impact of co-administration of *Na*-GST-1 and *Na*-APR-1 (M74) on the affinity of the antibody interactions with both recombinant antigens.
5. To assess the impact of co-administration of *Na*-GST-1 and *Na*-APR-1 (M74) on the production of memory B cells specific for each antigen.

Description of Study Design:

Double blind, randomized, controlled, dose-escalation Phase 1 clinical trial in hookworm exposed adults living in the area of Americaninhas, Minas Gerais, Brazil. Subjects will receive three

doses of the assigned vaccine delivered intramuscularly on approximately Days 0, 56, and 112.

Safety will be measured from the time of each study vaccination (Day 0) through 14 days after each study vaccination by the occurrence of solicited injection site and systemic reactogenicity events.

Unsolicited non-serious adverse events (AEs) will be collected from the time of the first study vaccination through approximately 1 month after each study vaccination. New-onset chronic medical conditions and Serious Adverse Events (SAEs) will be collected from the time of the first study vaccination through approximately 9 months after the third study vaccination (final visit). Clinical laboratory evaluations for safety will be performed on venous blood collected approximately 14 days after each vaccination.

Immunogenicity testing will include IgG antibody responses to each vaccine antigen, by an indirect enzyme-linked immunosorbent assay (ELISA) and also by ImmunoCAP, on serum obtained prior to each study vaccination and at time points after each vaccination (see Appendix A); antibody affinity by Surface Plasmon Resonance; functional activity of vaccine-induced antibodies via *in vitro* enzyme neutralization assays; and, antigen-specific memory B cell responses.

Recruitment and enrollment into the study will occur on an ongoing basis, with each group being recruited and vaccinated in sequence.

60 subjects will be enrolled into 6 groups of 10:

The first 20 subjects will be entered into Groups 1 and 2 through open sequential enrollment.

- Group 1 double-blind IP allocation (n=10):

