 - 5 subjects will receive 10µg Na-APR-1 (M74) delivered by IM injection in the deltoid muscle, with sterile saline administered to the alternate arm.
 - 5 subjects will receive 10µg Na-APR-1 (M74) delivered by IM injection in the deltoid muscle, with 100µg Na-GST-1 administered to the alternate arm.
- Group 2 double-blind IP allocation (n=10):
 - 5 subjects will receive 10µg Na-APR-1 (M74) plus 5µg GLA-AF delivered by IM injection in the deltoid muscle, with sterile saline administered to the alternate arm.
 - 5 subjects will receive 10µg Na-APR-1 (M74) plus 5µg GLA-AF delivered by IM injection in the deltoid

muscle, with 100µg *Na*-GST-1 administered to the alternate arm.

The next 20 subjects will be entered into Groups 3 and 4 through open sequential enrollment.

- Group 3 double-blind IP allocation (n=10):
 - 5 subjects will receive 30µg *Na*-APR-1 (M74) delivered by IM injection in the deltoid muscle, with sterile saline administered to the alternate arm.
 - 5 subjects will receive 30µg *Na*-APR-1 (M74) delivered by IM injection in the deltoid muscle, with 100µg *Na*-GST-1 administered to the alternate arm.
- Group 4 double-blind IP allocation (n=10):
 - 5 subjects will receive 30µg *Na*-APR-1 (M74) plus 5µg GLA-AF delivered by IM injection in the deltoid muscle, with sterile saline administered to the alternate arm.
 - 5 subjects will receive 30µg *Na*-APR-1 (M74) plus 5µg GLA-AF delivered by IM injection in the deltoid muscle, with 100µg *Na*-GST-1 administered to the alternate arm.

The final 20 subjects will be entered into Groups 5 and 6 through open sequential enrollment.

- Group 5 double-blind IP allocation (n=10):
 - 5 subjects will receive 100µg *Na*-APR-1 (M74) delivered by IM injection in the deltoid muscle, with sterile saline administered to the alternate arm.
 - 5 subjects will receive 100µg *Na*-APR-1 (M74) delivered by IM injection in the deltoid muscle, with 100µg *Na*-GST-1 administered to the alternate arm.
- Group 6 double-blind IP allocation (n=10):
 - 5 subjects will receive 100µg *Na*-APR-1 (M74) plus 5µg GLA-AF delivered by IM injection in the deltoid muscle, with sterile saline administered to the alternate arm.
 - 5 subjects will receive 100µg *Na*-APR-1 (M74) plus 5µg GLA-AF delivered by IM injection in the deltoid muscle, with 100µg *Na*-GST-1 administered to the alternate arm.

[figure not shown]
Estimated Time to Complete Enrollment:

3 months

Schematic of Study Design:

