3.2.4 Exploratory Outcome Measures

The following parameter will be evaluated for each dose and formulation of *Na*-APR-1 (M74) alone or co-administered with *Na*-GST-1:

1. Cellular immune responses following vaccination.

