11.3 Planned Interim Analyses

11.3.1 Safety Review

Descriptive and hypothesis-testing approaches will be used to estimate AE rates and to compare these rates in the difference doses and formulations of *Na*-APR-1 (M74) alone or co-administered with *Na*-GST-1. Estimates will be presented with their 95% confidence intervals. Formal statistical tests, as outlined below, will be used to compare doses. No formal adjustments for multiple comparisons will be made. Statistical tests will use a two-sided significance level of 5%.

The proportion of subjects with at least one injection site AE will be compared by vaccine allocation (e.g., *Na*-APR-1 (M74) vs. *Na*-APR-1 (M74) co-administered with *Na*-GST-1), by *Na*-APR-1 (M74) dose, and by GLA-AF dose.

Laboratory results (hematological and clinical chemistry) will be examined for trends over time and any clinically significant values for individuals will be reported.

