11.3.2 Immunogenicity Review

The proportion of subjects with detectable anti-*Na*-GST-1 and anti-*Na*-APR-1 (M74) responses, and the duration of responses, will be summarized as descriptive measures. Geometric mean antibody responses will be compared between Groups with comparisons made by analysis of variance (ANOVA) tests and pair-wise comparisons by contrasts. Antibody responses will be measured at Days 0, 7, 14, 28, 56, 63, 70, 84, 112, 119, and 126 for interim analysis, with Days 140, 200, 290, and 380 added for final analysis.

To exploit the multiple measures of antibody within each subject, a longitudinal model may be built (if possible) to describe the antibody responses over time. The models will explore if there are any differences between those administered *Na*-APR-1 (M74)/Alhydrogel[®] alone and those co-administered *Na*-GST-1/Alhydrogel[®].

Summary statistics will be used to present exploratory study results of the cellular immune responses to *Na*-GST-1 and *Na*-APR-1 (M74) before and after immunization. To assess the changes in lymphocyte proliferative responses and cytokine/chemokine profiles over time, a generalized estimating equations model with robust standard errors will be constructed. When necessary, data reduction approaches will be used.

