2. The IgG level by ImmunoCAP on approximately Day 126.

Analysis Plan:

- a. The proportion of participants with detectable anti-Na-GST-1 and anti-Na-APR-1 (M74) responses will be summarized as a descriptive measure.
- b. IgG levels will be displayed graphically by study group using notched box plots.
- c. Geometric mean antibody responses will be compared between vaccine formulation and dose groups. Comparisons between groups will be made by a one-way analysis of variance (ANOVA) with pair-wise comparisons between groups made by contrasts.
- d. Geometric mean antibody responses for each antigen will be compared using a regression model with main effects for the doses of Na-APR-1 (10, 30 or 100µg), GLA-AF (0 or 5 µg), and Na-GST-1 (0, 100µg).
- e. For antigen-specific log IgG levels, a three-way ANOVA will be conducted, with Na-GST-1, Na-APR (M74) and GLA-AF doses as factors.
- f. Pair-wise comparisons across all combinations of Na-APR-1 (M74) doses, GLA-AF doses (i.e., 0 or 5 µg), and Na-GST-1 co-administration status will be assessed using Tukey's HSD.

Tertiary Objective 1: To assess the impact of co-administration of Na-GST-1 on the duration of the antibody responses to Na-APR-1 (M74), and vice versa.

Tertiary Outcome Measure 1: The IgG antibody response, by an indirect enzyme-linked immunosorbent assay (ELISA) at approximately 7, 14, and 28 days after each vaccination, and approximately 3, 6, and 9 months after the third dose.

Tertiary Outcome Measure 2: The IgG antibody response, by ImmunoCAP at approximately 7, 14, and 28 days after each vaccination, and approximately 3, 6, and 9 months after the third dose.

Analysis Plan:

- a. The proportion of participants with detectable anti-Na-GST-1 and anti-Na-APR-1 (M74) responses will be summarized as a descriptive measure.
- b. Antigen-specific IgG levels will be displayed graphically by study group using notched box plots at each time point.

-
- c. Geometric mean antibody responses will be compared between vaccine formulation and dose groups at each time point. Comparisons between groups will be made by a one-way analysis of variance (ANOVA) with pair-wise comparisons between groups made by contrasts.
 - d. Percent change in IgG antibody levels from days of vaccination to days 7,14 and 28 will be compared between vaccine formulation and dose groups. Values will be reported with 95% confidence intervals.

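### The robust-standard-error GEE planned for the exploratory cellular responses needs a small-sample correction: uncorrected, a nominal 5% test runs at about 15% within a cell of 5 and about 12% for 5 vs 5

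*Protocol*

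**What the plan says.** Section 11.3.2 covers the cellular responses in two steps. First, "Summary statistics will be used to present exploratory study results of the cellular immune responses" before and after immunization. Second, to assess change over time in proliferation and in cytokine and chemokine profiles, "a generalized estimating equations model with robust standard errors will be constructed". It gives no working correlation, unit of fitting, contrast, reference distribution or small-sample correction.

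Section 3.2.4 sets the level of evaluation: "The following parameter will be evaluated for each dose and formulation of" Na-APR-1 (M74), alone or co-administered with Na-GST-1. The Protocol Summary gives the sizes: "60 subjects will be enrolled into 6 groups of 10", and each group is split in two, for example "5 subjects will receive 10µg Na-APR-1 (M74) delivered by IM injection in the deltoid muscle, with sterile saline" and 5 with Na-GST-1. Three doses, two formulations and two co-administration states make 12 cells of 5.

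Sections 11.3.1 and 11.4 set tests at two-sided 5% and estimates with 95% confidence intervals. For the tertiary longitudinal outcomes, section 11.4 uses Proc Mixed. For cytokines and chemokines in the final analysis it names only a longitudinal panel analysis, without the estimation method.

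**The concern.** The sandwich estimator takes the variance from the residuals of independent subjects. With few subjects it is biased low, and standard software refers the Wald statistic to a normal or chi-square distribution. Both faults act in the same direction, so intervals are too narrow and tests reject too often. With 5 subjects per cell, the level at which the outcome is to be evaluated, the effect is large. Chance shifts in cytokine levels or proliferation could then be reported as responses to vaccination or as effects of co-administration. An unpowered exploratory trial depends on its intervals being honest, so low power does not excuse under-coverage.

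**Working it through.** **Inputs.** Two-sided 5% level (sections 11.3.1 and 11.4). Cells of 5, 60 subjects in all (Protocol Summary, section 4). Cellular blood draws at 15 visits, of which 11 fall up to Day 126 (sections 7.2 to 7.4). The protocol gives no variance, within-subject correlation or visit coding for these assays. I assume normal data on the analysis scale, no dropout, and in the simulations an exchangeable correlation of 0.3 to 0.6.

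**The plan's own figures.** The protocol states no error rate for this model. Its only numerical design figures, the event-detection probabilities in section 11.2, reproduce: for example 1 - 0.90^20 = 87.84%.

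**Single contrast, balanced cells.** The uncorrected sandwich divides by n instead of n - 1, and the test uses 1.96. The true size is therefore

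P(|t_df| > 1.96 x sqrt((n-1)/n)), with df = n - 1 within one cell and df = 2n - 2 between two cells.

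At n = 5 the threshold is 1.96 x sqrt(4/5) = 1.753.

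| n per cell | change within a cell | between two cells |
|---|---|---|
| 5 | 15.4% | 11.8% |
| 10 | 9.6% | 7.9% |
| 30 | 6.4% | 5.9% |

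The correct t critical value on 4 df is 2.776, so the within-cell interval at n = 5 has 1.753/2.776 = 63% of the width it should have.

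**Simulation check.** With 4 or 8 visits and an independence working correlation, the size was 15.0-16.0% for the within-cell slope and 11.8-12.0% for 5 vs 5. A packaged GEE with exchangeable correlation and 6 visits (600 replicates, so rougher) gave 17.5% for the within-cell slope, 11.7% for arm and 14.7% for arm by time.

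**One model on all 60 subjects, single contrast.** With main effects the size is 5.5-5.8% for the pooled time slope, 5.5-6.0% for co-administration by time, and 6.4-6.8% for co-administration. If the same 60 subjects are modelled with cell-specific slopes, the uncorrected sandwich is no better than separate fits: 14.9-15.4% for one cell's slope and 10.8-11.7% for a difference between two cells.

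**Joint test over categorical visits, pooled.** The robust Wald statistic is then a Hotelling statistic multiplied by n/(n-1) and referred to chi-square on p = visits - 1.

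- All 60, 11 visits (p = 10): chi-square limit 18.307. F limit = 18.307 x (59/60) x 50/(10 x 59) = 1.526. P(F(10,50) > 1.526) = 15.8%.
- All 60, 15 visits (p = 14): chi-square limit 23.685. F limit = 23.685 x (59/60) x 46/(14 x 59) = 1.297. P(F(14,46) > 1.297) = 24.6%.
- Co-administration by time, 30 vs 30: 17.0% with 11 visits and 26.4% with 15.
- Within a cell of 5 the sandwich has rank at most 4, so a joint test of 10 or 14 contrasts cannot be computed. With 4 visits (p = 3) its size is 52%.

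**Effect of correcting only the variance.** With a bias-reduced sandwich but still a normal reference, the packaged GEE at 5 vs 5 gave 6.0% (arm), 8.2% (arm by time) and 11.5% (within-cell slope).

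**The case against.** The strongest reply is that the protocol does not fix the worst case. Section 11.3.2 names the model and its standard errors. It does not say that it is fitted cell by cell, that a normal reference is used, or that no correction applies. Section 11.4 defers full methods to a separate analytical plan, where such detail commonly sits. That stands: 15% and 12% describe what happens if the named method is applied uncorrected at the level set in section 3.2.4, and they are not error rates written into the plan. It is also true that a single contrast in a pooled main-effects model is only mildly affected. Pooling does not protect a joint test over many visits, however, or cell-specific slopes.

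A second reply is that the between-arm comparison of cytokines and chemokines in section 11.4 is a longitudinal panel analysis, which need not be a GEE. This too stands, and it limits the between-cell figures to use of the section 11.3.2 model for that purpose.

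Third, little depends on the result. The hypotheses are assessed mainly by descriptive statistics (section 11.1), the trial is not powered for group differences (section 11.2), and the interim report on which the paediatric decision rests uses safety and ELISA IgG data (section 15.4). This sets the weight of the point but does not remove it.

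A reader might also infer that the notched box plots carry a false-positive rate of about 12%, because notches are likewise a large-sample device. The documents do not support that. Section 11.4 says only that "IgG levels will be displayed graphically by study group using notched box plots". No decision rule attaches to notch overlap, and inference on the same IgG data is by ANOVA contrasts and Tukey's HSD. The 12% itself needs boxes of 5 and particular quartile definitions. Others give 0.5-3.3% at n = 5, and boxes of 10 give 3.9-4.7%.

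**Conclusion.** The point holds for the GEE, as a minor one. A robust-standard-error GEE is poorly suited to cells of 5. Without a small-sample correction, a nominal 5% test rejects about 15% of the time for change within a cell and about 12% for 5 vs 5. With all 60 subjects in a main-effects model, one contrast is nearly right (about 5.5-7%), while a joint test over categorical visits is about 16% (11 visits) to 25% (15 visits). The cell-level figures assume an uncorrected sandwich with a normal reference, and the joint-test figures a chi-square reference with visit coded as categorical. All assume approximately normal data and no dropout. None of these choices is stated in the protocol. No primary or secondary analysis is affected, and the notched plots form no part of the conclusion.

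**What to change.** In section 11.3.2, replace the robust-standard-error GEE by the Proc Mixed approach that section 11.4 already plans for the tertiary outcomes, with Kenward-Roger degrees of freedom. Fit it once to all 60 subjects and obtain the cell results as contrasts. Name the same model for the cytokine and chemokine panel analysis in section 11.4, so that interim and final analyses agree.

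If GEE is kept, state a bias-corrected sandwich (for example Mancl-DeRouen), a t or F reference distribution, and a small number of pre-stated time contrasts in place of a joint test over all visits. Correcting the sandwich alone is not enough at n = 5, as the remaining 11.5% for within-cell change shows.

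The cost is a change of wording and programming, and somewhat wider intervals. No data collection or sample size changes.

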11.4 Final Analysis Plan

The purpose of this trial is to estimate AE rates and patterns of immune response as well as to compare these rates and patterns between the investigational vaccines, when they are administered separately or when they are co-administered.

This section briefly describes the statistical methods to be used; a detailed analytical plan will fully describe the methods. The analytical plan will discuss the planned approaches to missing data. Deviations from the original analytical plan will be thoroughly documented and reported to the Sponsor.

Descriptive and hypothesis-testing approaches will be used to meet the protocol objectives as stated in **Section 3**. Estimates will be presented with their 95% confidence intervals. Formal statistical tests, as outlined below, will be used to compare doses. Statistical tests will use a two-sided significance level of 5%.

Note: For the analyses described below, historical safety data from a Phase 1 clinical trial conducted at the same study site and in the same subject population (study SVI-10-01, see **Section 2.1.6** above for a description of this trial) will be used to obtain a comparison of *Na*-GST-1/Alhydrogel. As well, stored serum and cell specimens from those study participants will be used in the immunological assays to obtain data on subjects administered *Na*-GST-1/Alhydrogel without co-administered *Na*-APR-1 (M74). These specimens from SVI-10-01 will be assayed at the same time as those newly collected from the study described in this protocol.

Primary Objective: To evaluate the safety and reactogenicity of three different dose concentrations of Na-APR-1 (M74) adjuvanted with Alhydrogel® or Alhydrogel® plus GLA-AF and administered either with or without Na-GST-1, in healthy Brazilian adults.

AEs will be coded according to Medical Dictionary of Regulatory Activities (MedDRA™) preferred terms. The frequency, severity, and relationship of AEs per each vaccine formulation and dose cohort of Na-APR-1 (M74) and co-administration status with Na-GST-1 will be presented in tabular form using the MedDRA™ coded term and organized by MedDRA™ System, Organ, and Class (SOC) designations.

- The frequency of immediate, systemic, and local injection site AEs will be summarized by SOC and preferred term.
- Line listings of clinical and laboratory AEs classified as immediate (within the first 60 minutes), systemic, and local will be displayed in tables stratified by dose cohort and formulation of Na-APR-1 (M74) and formulation (i.e., no GLA-AF or 5 µg GLA-AF).
- AEs will be summarized by severity and relationship to vaccine formulation by individuals and dose of Na-GST-1, Na-APR-1 (M74), and GLA-AF.
- The frequency of vaccine-related SAEs will be tallied as well as summarized by body system, by vaccine formulation and dose cohort.

Primary Outcome Measures:

The following summary parameters will be evaluated for each dose and formulation of Na-APR-1 (M74) alone or co-administered with Na-GST-1:

1. Frequency of solicited injection site and systemic reactogenicity, graded by severity, on the day of each study vaccination through 14 days after each study vaccination.
2. Frequency of study vaccine-related serious adverse events from the time of the first study vaccination through approximately 9 months after the last study vaccination.
3. Frequency of clinical safety laboratory adverse events.
4. Frequency of unsolicited adverse events, graded by severity, from the time of each study vaccination through approximately 1 month after each study vaccination.
5. Frequency of new-onset chronic medical conditions through approximately 9 months after the third study vaccination.
6. Frequency of Adverse Events of Special Interest through approximately 9 months after the third study vaccination.

Analysis Plan:

The proportion of participants with at least one injection site AE will be compared by Na-APR-1 (M74) vaccine formulation and dose cohort and co-administration status with Na-GST-1. We will test the null hypotheses that the type and number of adverse events is the same across all groups by Fisher's exact test.

Laboratory results (hematological and clinical chemistry) will be examined for trends over time and any clinically significant values for individuals will be reported.

Secondary Objective: To assess the impact of co-administering Na-APR-1 (M74) and Na-GST-1 on antibody production by measuring the antibody levels to each antigen on study Day 126.

Secondary Outcome Measures:

The following parameters will be evaluated for each dose and formulation of Na-APR-1 (M74) alone or co-administered with Na-GST-1:

1. The IgG level by an indirect enzyme-linked immunosorbent assay (ELISA) on approximately Day 126.
2. The IgG level by ImmunoCAP on approximately Day 126.

Analysis Plan:

- a. The proportion of participants with detectable anti-Na-GST-1 and anti-Na-APR-1 (M74) responses will be summarized as a descriptive measure.
- b. IgG levels will be displayed graphically by study group using notched box plots.
- c. Geometric mean antibody responses will be compared between vaccine formulation and dose groups. Comparisons between groups will be made by a one-way analysis of variance (ANOVA) with pair-wise comparisons between groups made by contrasts.
- d. Geometric mean antibody responses for each antigen will be compared using a regression model with main effects for the doses of Na-APR-1 (10, 30 or 100µg), GLA-AF (0 or 5 µg), and Na-GST-1 (0, 100µg).
- e. For antigen-specific log IgG levels, a three-way ANOVA will be conducted, with Na-GST-1, Na-APR (M74) and GLA-AF doses as factors.
- f. Pair-wise comparisons across all combinations of Na-APR-1 (M74) doses, GLA-AF doses (i.e., 0 or 5 µg), and Na-GST-1 co-administration status will be assessed using Tukey's HSD.

Tertiary Objective 1: To assess the impact of co-administration of Na-GST-1 on the duration of the antibody responses to Na-APR-1 (M74), and vice versa.

Tertiary Outcome Measure 1: The IgG antibody response, by an indirect enzyme-linked immunosorbent assay (ELISA) at approximately 7, 14, and 28 days after each vaccination, and approximately 3, 6, and 9 months after the third dose.

Tertiary Outcome Measure 2: The IgG antibody response, by ImmunoCAP at approximately 7, 14, and 28 days after each vaccination, and approximately 3, 6, and 9 months after the third dose.

Analysis Plan:

- a. The proportion of participants with detectable anti-Na-GST-1 and anti-Na-APR-1 (M74) responses will be summarized as a descriptive measure.
- b. Antigen-specific IgG levels will be displayed graphically by study group using notched box plots at each time point.

-
- c. Geometric mean antibody responses will be compared between vaccine formulation and dose groups at each time point. Comparisons between groups will be made by a one-way analysis of variance (ANOVA) with pair-wise comparisons between groups made by contrasts.
 - d. Percent change in IgG antibody levels from days of vaccination to days 7,14 and 28 will be compared between vaccine formulation and dose groups. Values will be reported with 95% confidence intervals.
 - e. Percent change in IgG antibody levels from vaccination day #1 to #2, and from vaccination day #2 to #3 will be compared between vaccine formulation and dose groups to assess the sustainability of the response from trough to trough. Values will be reported with 95% confidence intervals.
 - f. Percent change in IgG antibody levels from the peak following the third vaccination, to 3, 6 and 9 months after the third vaccination. Values will be reported with 95% confidence intervals.
 - g. Geometric mean antibody responses for each antigen will be compared using a regression model at each time point with main effects for the doses of Na-APR-1 (M74) (10, 30 or 100µg), GLA-AF (0 or 5µg), and Na-GST-1 (0, 100µg)
 - h. For antigen-specific log IgG levels, three-way ANOVAs will be conducted, with Na-APR-1 (M74) dose, GLA-AF dose, and Na-GST-1 co-administration status as factors.
 - i. A longitudinal model will be built to describe the IgG levels over time. Using a longitudinal panel model, differences in antibody isotype levels by dose and formulation of Na-APR-1 (M74) and Na-GST-1 co-administration status will be explored. This will be accomplished using Proc Mixed in SAS 9.3 so the analysis will take account of the correlation between measurements on the same participant.

Tertiary Objective 2: To assess the impact of co-administration of Na-GST-1 on the distribution of IgG subclass responses to Na-APR-1 (M74) and vice versa.

Tertiary Outcome Measure 3: The IgG subclass distribution (IgG1, IgG3, and IgG4) by plate based ImmunoCAP on approximately Day 126.

Tertiary Outcome Measure 4: The IgG subclass distribution by plate based ImmunoCAP each day of vaccination, approximately 28 days later, and approximately 3 and 6 months after the final vaccination.

Analysis Plan:

- a. The proportion of subjects with detectable anti-Na-GST-1 and anti-Na-APR-1 (M74) IgG subclass responses will be summarized at each time point as a descriptive measure.
- b. IgG subclass antibody levels will be displayed graphically by study group using notched box plots at each time point.
- c. Geometric mean antibody responses will be compared between vaccine formulation and dose groups. Comparisons between groups will be made by a one-way analysis

-
- of variance (ANOVA) with pair-wise comparisons between groups made by contrasts.
- d. For antigen-specific IgG subclass (IgG1-IgG4) levels, a three-way ANOVA will be conducted, with Na-APR-1 (M74) and GLA-AF doses, and Na-GST-1 co-administration status, as factors.
 - e. A longitudinal model will be built to describe each of the antibody isotype levels over time for each of IgG1-IgG4. Using a longitudinal panel model, differences in antibody isotype levels by dose and formulation of Na-APR-1 (M74) and Na-GST-1 co-administration status will be explored. This will be accomplished using Proc Mixed in SAS 9.3 so the analysis will take account of the correlation between measurements on the same participant.

Tertiary Objective 3: To assess the impact of co-administration of Na-GST-1 and Na-APR-1 (M74) on the functional capacity of vaccine-induced antibodies to neutralize the *in vitro* activity of the native enzymes (Na-GST-1 and wild type Na-APR-1).

Tertiary Outcome Measure 5: The functional capacity of vaccine-induced antibodies to neutralize the *in vitro* activity of the native enzymes.

Analysis Plan:

- a. Percent inhibition of native enzyme activity will be displayed graphically for the various study groups at each time point.
- b. Three-way ANOVAs with Na-APR-1 (M74), Na-GST-1, and GLA-AF as factors and percent inhibition as the outcome will be estimated.
- c. A longitudinal model will be built to describe percent inhibition of native enzyme activity over time. Using a longitudinal panel model, differences in percent inhibition by dose and formulation of Na-APR-1 (M74) and co-administration with Na-GST-1 will be explored. This will be accomplished using Proc Mixed in SAS 9.3, so the analysis will take account of the correlation between measurements on the same participant.

Tertiary Objective 4: To assess the impact of co-administration of Na-GST-1 and Na-APR-1 (M74) on the affinity of the antibody interactions with both recombinant antigens.

Tertiary Outcome Measure 6: The affinity of the antibody interactions with both recombinant antigens at approximately 7, 14, and 28 days after each vaccination, and 3, 6, and 9 months after the third dose.

Analysis Plan:

- a. Antibody affinity will be displayed graphically for the various study groups at each time point.
- b. Three-way ANOVAs with Na-APR-1 (M74), Na-GST-1, and GLA-AF as factors and overall affinity as the outcome will be estimated.

- c. A longitudinal model will be built to describe increasing antibody affinity (affinity maturation) over time. Using a longitudinal panel model, differences in affinity maturation by dose and formulation of *Na*-APR-1 (M74) and co-administration with *Na*-GST-1 will be explored. This will be accomplished using Proc Mixed in SAS 9.3, so the analysis will take account of the correlation between measurements on the same participant.

Tertiary Objective 5: To assess the impact of co-administration of *Na*-GST-1 and *Na*-APR-1 (M74) on the production of memory B cells specific for each antigen.

Tertiary Outcome Measure 7: The production of memory B cells specific for each antigen on days of vaccination, approximately 28 days following each vaccination, and 6 and 9 months after the third dose.

Analysis Plan:

- a. The amount of *Na*-GST-1 and *Na*-APR-1 (M74) specific memory B cells will be expressed as a percentage of total lymphocytes present in the blood.
- b. The percentage of specific memory B cells will be displayed graphically by study group at each time point.
- c. Two separate longitudinal panel analyses will test the null hypothesis that average percentages for each of memory B cells are the same in *Na*-APR-1 (M74) groups with and without co-administration of *Na*-GST-1 over time. This will be accomplished using Proc Mixed in SAS 9.3 so the analysis will take account of the correlation between measurements on the same participant.
- d. Mann-Whitney tests will assess the null hypothesis that cytokine levels are the same in the groups at the primary time point of Day 126, two weeks after final vaccination.

Exploratory Objective: To assess the cellular immune responses to the *Na*-GST-1 and *Na*-APR-1 (M74) antigens following immunization.

The following assays will be performed to assess the cellular immune responses to vaccination with *Na*-APR-1 (M74) +/- *Na*-GST-1:

- a. Lymphocyte proliferative responses to *in vitro* stimulation with *Na*-GST-1 or *Na*-APR-1 (M74).
- b. Cytokine and chemokine production *in vitro* in response to stimulation with *Na*-GST-1 or *Na*-APR-1 (M74).
- c. Changes in *in vivo* PBMC subpopulations as determined by flow cytometry.
- d. A longitudinal panel analysis will test the null hypothesis that cytokine and chemokine levels are the same when *Na*-APR-1 (M74) is administered with and without or *Na*-GST-1 and examine for trends over time.

Should the study be terminated early, the investigative team will discuss with the SMC the reason for termination and determine which study questions can be addressed in an unbiased manner with the available data. The available data will be analyzed and interpreted in light of early termination.

